#### Display of results

Parameters estimated from the selected model will be presented with their standard error and 95% confidence interval.

$\Delta\Delta\text{QTc}$  predicted for each dose level will be presented with their 2-sided 90% confidence interval and a graphical display of predicted  $\Delta\Delta\text{QTc}$  over the concentration range collected during the study will also be provided.

#### Decision rule

The impact of P03277 on QT/QTc prolongation will be considered as below the threshold of regulatory concern if the upper bound of the 90% confidence interval of  $\Delta\Delta\text{QTc}$  predicted at supra-clinical dose  $C_{\text{max}}$  is below 10 ms.

#### 5.5.4.4 Morphological analysis

Analysis of morphology will be based on the number of subjects with at least one emergent abnormality. The number (%) of subjects having changes from baseline will be summarized by the finding's conclusion (see Appendices) for each trial product. Localization will be taken into account. The table will exclude reported statement associated to a normal ECG if necessary:

Category	Term includes:
Q or QS pattern	Small Q waves in inferior leads, consider normal variant
Axis and Voltage	Poor Precordial R wave progression, consider normal variant
Axis and Voltage	Abnormal P wave axis, consider normal variant
Hypertrophy	Left ventricular hypertrophy by QRS voltage consider normal variant
ST depression and elevation	ST elevation, consider normal variant
ST depression and elevation	Early repolarization, consider normal variant
T/U wave abnormalities	Normal repolarization pattern
T/U wave abnormalities	U wave, consider normal variant
AV conduction	First degree AV block, consider normal variant
AV conduction	Short PR interval, consider normal variant
Intraventricular conduction defects	Incomplete RBBB, consider normal variant (QRS $\leq$ 120msec)
Rhythm	Normal sinus rhythm, rate 50-100 bpm
Rhythm	Possible normal sinus rhythm, rate 50-100 bpm
Rhythm	Dominant sinus rhythm
Rhythm	Uncertain supraventricular rhythm, consider normal variant
Rhythm	Respiratory sinus arrhythmia
Rhythm	Respiratory sinus arhythmia, consider normal variant
Rhythm	Sinus tachycardia, rate 100-130 bpm, consider normal variant
Rhythm	Sinus bradycardia, rate 40-49 bpm, consider normal variant
Rhythm	Wandering atrial pacemaker, consider normal variant, unsinusual rhythm
Rhythm	Atrial electronic pacemaker

CONFIDENTIAL	STATISTICAL ANALYSIS PLAN N° GDX-44-006  VERSION N° 2.0      DATED: 24JUL2018  [REDACTED]	[REDACTED]  Page 33 / 57
--------------	---	--------------------------------

Rhythm	Atrial electronic pacemaker, intermittent
Rhythm	Ventricular electronic pacemaker, unsinusual rhythm
Rhythm	Ventricular electronic pacemaker, intermittent, unsinusual rhythm
Rhythm	Dual chamber electronic pace maker
Rhythm	Dual chamber electronic pace maker, intermittent

## 5.6. Safety evaluation

### 5.6.1. Extent of exposure

Duration between trial products administration and end of period, summary of durations during the study, volume theoretically administered, volume actually administered, dose actually administered, actual rate of administration, volume of saline flush, location of injection site, mode of injection and occurrence of an overdose will be tabulated. Frequency tabulation of actual injection rate will be also displayed per trial product group and overall.

Body weight measured at inclusion visit and after each trial product administration (i.e. before the next administration) will be presented by each trial product group and overall.

The extent of exposure summary will be presented using the Safety Set.

Listing of exposure will be presented in CSR appendix 16.2.5.

### 5.6.2. Adverse events

All analyses of AEs will be based on the number of subjects with AEs (and not on the number of AEs) except otherwise specified and using the safety set.

Adverse events (AEs) will be coded using MedDRA version 21.0.

The time period for the assessment of AEs will be divided into 5 mutually exclusive and exhaustive periods:

- Before IMP/AMP: between informed consent signature and start of the first administration
- Period 1: between start of the first administration and start of the second administration
- Period 2: between start of the second administration and start of the third administration
- Period 3: between start of the third administration and start of the fourth administration
- Period 4: between start of the fourth administration and Day 12 included (date of Day 12 corresponds to date of Day 10 + 2 days not taking into account the time)
- After confinement period: during follow-up periods (> Day 12).

Events will be classified by trial products according to time of onset in the corresponding cycle related to trial products.

Events will be classified as treatment-emergent if they have started since the first administration.

Partial start dates/times will be queried. If information is not available to reliably allocate to a session and period, the allocation will be agreed at the data review meeting before database lock. If there is any doubt about treatment emergence, AEs will be classified as treatment emergent.

CONFIDENTIAL	
STATISTICAL ANALYSIS PLAN N° GDX-44-006
 
VERSION N° 2.0      DATED: 24JUL2018
 
██████████
	
██████████
 
Page 34 / 57

--------------	--	---

The number (%) of subjects having at least one AE as follows will be summarized for each trial product and overall for:

- At least one TEAE
- At least one AE with each of the following classification of intensity
  - Mild
  - Moderate
  - Severe
- At least one adverse reaction (relationship to trial treatment classified as ‘Related’)
- At least one AE with each of the following classifications of action taken with trial treatment:
  - Dose not changed
  - Trial product withdrawn
- At least one AE with each of the following classifications of outcome:
  - Recovered/resolved
  - Recovered/resolved with sequelae
  - Not recovered/Not resolved
  - Fatal

The table will show the same information for serious AE, defined as AEs with serious classified as ‘yes’ or missing. The table will be repeated for all TEAEs.

A table will be presented showing the total numbers of AEs and SAEs and the distribution of AEs (number [%] of subjects with number of AEs) for each IMP/AMP and overall. The table will also show the same information for SAEs defined as TEAEs with serious classified as ‘yes’ or missing, unless the number of SAEs make this uninformative.

Summaries by SOC and PT will be presented for all treatment-emergent events and all related treatment-emergent events for each IMP/AMP and overall.

Adverse events during follow-up period will be presented overall by SOC and PT.

Data listings will present all AEs reported, including non-TEAEs. Adverse event listings will be sorted by subject number and will display also the study procedure, body system, and preferred term, time of onset, duration, intensity, seriousness, outcome, relationship to the IMP/AMP, relationship to a study procedure, action taken with IMP/AMP, IMP unblinding, AE-targeted medication, other AE-targeted action, date and time of IMP/AMP administration (presented in CSR appendix 16.2.7).

AE Duration will be computed in days as Date of End of AE - Date of Onset of AE + 1. Date and time of administration displayed will be those of trial product administration preceding the date and time of onset of the AE. If the AE started before Day 1 or after the follow-up period, no date and time of administration will be displayed.

### **5.6.3. Deaths, serious adverse events and other significant adverse events**

All deaths, all serious adverse events and all adverse events of special interest experienced during the treatment period related to the study drug will be separately listed per subject number, presenting: first/last application, treatment phase (Initial or Follow-up), emergence, description, SOC, preferred

term, start and end date, duration, the relationship to study drug, the action taken and the seriousness criteria.

The list of preferred terms of adverse events of special interest is the following:

MedDRA Code	MedDRA Term
10076948	Acute encephalitis with refractory, repetitive partial seizures
10003628	Atonic seizures
10049612	Autonomic seizure
10075606	Change in seizure presentation
10053398	Clonic convulsion
10010920	Convulsions local
10010927	Convulsive threshold lowered
10079424	Focal dyscognitive seizures
10018100	Generalised tonic-clonic seizure
10067467	Nephrogenic systemic fibrosis
10061334	Partial seizures
10056209	Partial seizures with secondary generalisation
10076981	Post stroke seizure
10039906	Seizure
10071350	Seizure cluster
10040703	Simple partial seizures
10042772	Syncope
10043994	Tonic convulsion

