9.3.3 Adverse Events of Special Interest

An Adverse Event of Special Interest (AESI) is an AE designated by Guerbet for transmission to Pharmacovigilance in the same time frame as an SAE.

The list of AESI for this protocol is the following:

- Nephrogenic Systemic Fibrosis (NSF).
- Torsade de pointes
- Sudden death;
- Ventricular tachycardia;
- Ventricular fibrillation and flutter;
- Syncope (excluding vasovagal reaction due to blood sampling);
- Seizures

Also, any suspicion of transmission of an infectious agent via an IMP/AMP should be considered as a serious and processed as an SAE.

In addition, any adverse event resulting from an occupational exposure may be directly reported to Guerbet.

9.3.4 Any suspicion of transmission of an infectious agent via an IMP or moxifloxacin

Any suspicion of transmission of an infectious agent via an IMP or moxifloxacin should be considered as serious and processed as an SAE.

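### The SAP's AESI term list covers only 3 of the protocol's 7 AESI, its listing sentence can be read two ways, and its Safety Set omits the AMP

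*SAP*

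**What the plan says.** **AESI.** Protocol section 9.3.3 opens its list with "The list of AESI for this protocol is the following" and names seven items: nephrogenic systemic fibrosis (NSF), torsade de pointes, sudden death, ventricular tachycardia, "Ventricular fibrillation and flutter", syncope and seizures. SAP section 5.6.3 says "The list of preferred terms of adverse events of special interest is the following" and gives 18 MedDRA terms with codes.

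**Listing sentence.** After naming deaths and serious adverse events, SAP section 5.6.3 continues: "all adverse events of special interest experienced during the treatment period related to the study drug will be separately listed per subject number". The columns it then specifies include "treatment phase (Initial or Follow-up") and "the relationship to study drug, the action taken and the seriousness criteria".

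**Safety Set.** Protocol section 11.3.2 admits any subject who received at least one administration of IMP or AMP. SAP section 5.2 admits any subject who received at least one administration of IMP. SAP section 1.2 treats the three IMPs and the one AMP (moxifloxacin) as distinct products.

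**Versions.** SAP section 1 states that it rests on protocol version 4.0 with amendment 2. The protocol under review is version 5.0 with amendment 03, dated 31 August 2018; the SAP is dated 24 July 2018.

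**The concern.** A preferred-term list is what a programmer uses to flag AESI. If it is closed and incomplete, events in the missing categories are not flagged. In a study whose purpose is to assess effects on cardiac repolarisation, the missing categories are torsade, the two ventricular arrhythmia items and sudden death.

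The listing sentence adds uncertainty. The phrase about relation to the study drug may be a causality filter or may only describe timing, and two programmers could produce different listings from it. The restrictive reading would drop unrelated and follow-up AESI, which protocol sections 9 and 9.1.2 require to be recorded in follow-up whether related or not.

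The Safety Set wording matters because the SAP's AE tables use that set and are planned for every product, including moxifloxacin. A subject who received moxifloxacin and never an IMP would be excluded from the tables meant to describe moxifloxacin.

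**Working it through.** **1. Mapping the SAP terms to the protocol AESI**

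| Protocol 9.3.3 item | SAP 5.6.3 terms |
|---|---|
| Nephrogenic systemic fibrosis | 1 |
| Syncope | 1 |
| Seizures | 16 |
| Torsade de pointes | 0 |
| Sudden death | 0 |
| Ventricular tachycardia | 0 |
| Ventricular fibrillation and flutter | 0 |

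Total terms: 1 + 1 + 16 = 18, which is the whole SAP list. Categories covered: 3 of 7. Not covered: 7 − 3 = 4.

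**2. Could rows have been lost from the table?** The list is alphabetical and ends at Tonic convulsion, so torsade and the ventricular terms would come after the last visible row. Sudden death would not: it sorts between Simple partial seizures and Syncope, and it is absent there. The SAP's table of contents also puts section 5.6.4 on page 35, and the page 36 header comes only after the opening text of 5.6.4. The table therefore ends on the page where the next section starts, with no page break in which rows could have been lost.

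**3. Reading the listing sentence**

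- *Timing reading.* SAP section 5.6.2 uses a similar phrase purely for timing: "Events will be classified by trial products according to time of onset in the corresponding cycle related to trial products".
- *Restrictive reading.* Taken at face value, the phrase limits the listing to drug-related events in a treatment period.
- *Undefined period.* Treatment period is not among the periods that section 5.6.2 sets out, and those include a separate one, "After confinement period: during follow-up periods (> Day 12").
- *Conflict within the sentence.* A causality column and a column that distinguishes initial from follow-up phase would serve little purpose if only related, treatment-period events were listed.
- *Conflict with collection.* Protocol sections 9 and 9.1.2 have AESI recorded in follow-up, related or not.

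The restrictive reading is the weaker one, but the words allow it.

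**4. Size of the Safety Set difference**

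Inputs: 48 planned subjects, 12 per sequence, four sequences in a Williams design (protocol section 3.1); recruitment may stop once 40 subjects are evaluable (protocol section 11.2).

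- Each product comes first in exactly one of the four sequences. A subject dosed as randomised can be moxifloxacin-only only in the moxifloxacin-first sequence, so at most 12 of 48.
- Effect of one such subject on the overall denominator, and on the moxifloxacin denominator if all subjects received moxifloxacin: 1/48 = 2.1%.
- If recruitment stops at 40 evaluable subjects and the only other subject is this one: 1/(40 + 1) = 1/41 = 2.4%.
- In tables by sequence: 1/12 = 8.3% of that sequence.
- P03277 and placebo event counts do not change, because the subject received neither.

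The documents give no dropout rate, so no probability of such a subject can be stated.

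**The case against.** The strongest reply is that little would go unseen. The same sentence lists all deaths and all serious adverse events, and protocol section 9.2.1 counts life-threatening and important medical events as serious. A sudden death would therefore appear unless the restrictive reading is applied to deaths too. SAP section 5.6.2 lists every AE and tabulates treatment-emergent and follow-up events by SOC and preferred term. SAP section 5.5.4.4 counts emergent rhythm abnormalities on the extracted ECGs. Torsade, ventricular tachycardia and ventricular fibrillation/flutter are stopping events in protocol section 10.2, and reasons for discontinuation are reported. This stands, and it limits the loss to AESI identification, mainly for non-serious events.

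A second reply is that protocol version 4.0 is not supplied and the SAP's list of outputs and table shells are not visible; the SAP may have matched the protocol when it was written. This also stands. The finding is a misalignment with the current protocol, not proof of an undeclared change. Hidden shells might narrow the ambiguity of the listing sentence, but the term list and the Safety Set definition in the visible text would still need correcting.

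Third, the page 35 header is missing from the text, and three of the four missing categories sort after the last row, so truncation deserves a thought. The gap at Sudden death in the middle of the list answers this, although one could argue that sudden death was left out because deaths are listed anyway. A look at that page of the original would settle it.

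Fourth, the Safety Set point is hypothetical. It is, in that its effect is zero without a moxifloxacin-only subject. The definition is still wrong for tables planned for each IMP and AMP.

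**Conclusion.** The concern holds in all three parts. As written, the SAP has no AESI term for 4 of the protocol's 7 AESI. Its listing sentence is ambiguous on causality and period. Its Safety Set excludes a moxifloxacin-only subject whom the protocol includes.

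The consequence is moderate. Events are not lost from the report, but the AESI listing would fail to identify the cardiac events most relevant to a QT study. The Safety Set difference is 2.1% of 48 per affected subject (2.4% of 41, or 8.3% of one sequence of 12) and nil if there is none. The primary conclusion does not depend on any of this. The conclusion assumes that the term table is complete as shown and takes protocol version 5.0 as the reference. The SAP should be corrected.

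**What to change.** - **SAP section 5.6.3, term list:** add the preferred terms for torsade de pointes, sudden death, ventricular tachycardia, ventricular fibrillation and ventricular flutter, coded in the MedDRA version named in SAP section 5.6.2 (21.0).
- **SAP section 5.6.3, listing sentence:** state that all deaths, SAEs and AESI as collected, including those in follow-up, are listed regardless of causality. Keep the existing relationship and treatment-phase columns.
- **SAP section 5.2:** define the Safety Set by at least one administration of IMP or AMP, as in protocol section 11.3.2.
- **SAP section 1:** update the protocol version reference and check the rest of the SAP against version 5.0.

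The cost is a few words in three sections and a few added terms. No new data are needed and the primary analysis does not change.

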#### 5.6.4. Clinical laboratory evaluation

All laboratory values recorded during the study will be individually listed and flagged for values outside reference ranges and clinically significant (presented in CSR appendix 16.2.8). Laboratory data analysis will be done using the safety set and displayed by trial product group.

The baseline is defined as the last measure before the first trial product administration. The statistical analysis will present results in standard international (SI) units and conventional United States units (See Table 1 and Table 2 respectively). Original units will be only listed. Laboratory data will be analyzed quantitatively and qualitatively. Qualitative analyses will be done via comparison of laboratory data to their reference ranges. Quantitative analyses will be done by tabulating raw data and change from baseline. They will be displayed qualitatively as well by means of shift tables.

CONFIDENTIAL	STATISTICAL ANALYSIS PLAN N° GDX-44-006	██████████
	VERSION N° 2.0      DATED: 24JUL2018	Page 36 / 57
	██████████	

**Table 1 Hematology parameters**

Hematology parameters		SI Units	US Units
Basophils	BASO	10  /L	10  /μL
Basophils/Leukocytes	BASOLE	%	%
Eosinophils	EOS	10  /L	10  /μL
Eosinophils/Leukocytes	EOSLE	%	%
Hematocrit	HCT	v/v	%
Hemoglobin	HGB	g/L	g/dL
Lymphocytes	LYM	10  /L	10  /μL
Lymphocytes/Leukocytes	LYMLE	%	%
Mean red blood cells volume	MCV	fL	μm 
Monocytes	MONO	10  /L	10  /μL
Monocytes/Leukocytes	MONOLE	%	%
Neutrophils	NEUT	10  /L	10  /μL
Neutrophils/Leukocytes	NEUTLE	%	%
Platelet count	PLAT	10  /L	10  /μL
Red blood cells = Erythrocytes	RBC	10  /L	10  /μL
White blood cells = Leukocytes	WBC	10  /L	10  /μL

**Table 2 Biochemistry parameters**

Biochemistry parameters		SI Units	US Units
Magnesium*	MG	mmol/L	mg/dL
Sodium	SODIUM	mmol/L	mEq/L
Potassium	K	mmol/L	mEq/L
Chloride	CL	mmol/L	mEq/L
Glucose Random	GLUC	mmol/L	mg/dL
Urea Nitrogen	UREAN	mmol/L	mg/dL
Urea	UREA	mmol/L	mg/dL
Creatinine	CREAT	μmol/L	mg/dL
Protein	PROT	g/L	g/dL
Calcium	CA	mmol/L	mg/dL
Phosphorus	PHOS	mmol/L	mg/dL
Total bilirubin	BILI	μmol/L	mg/dL
Indirect Bilirubin	BILIND	μmol/L	mg/dL
Conjugated/Direct bilirubin	BILDIR	μmol/L	mg/dL
Aspartate amino transferase	AST	U/L	U/L
Alanine amino transferase	ALT	U/L	U/L
Alkaline phosphatase	ALP	U/L	U/L
Lactate dehydrogenase	LDH	U/L	U/L
Triglycerides	TRIG	mmol/L	mg/dL
eGFR*	GFRE	mL/min/1.73m 	mL/min/1.73m 

\* Magnesium and creatinine clearance from Cockcroft-Gault method measured only at screening visit.

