7.2.2.2 Biology

For each subject, blood samples will be performed at screening visit, at Day 1 and 2 days after each administration. The blood analysis will be performed by the site laboratory (except P03277 plasma and urine concentration assessment which will be managed by an analytical center)

The following parameters will be obtained and assessed:

- Hematology: Red Blood Cells (RBCs), White Blood Cells (WBCs), neutrophils, eosinophils, basophils, lymphocytes and monocytes, platelet count, hemoglobin, hematocrit, Mean red blood Cells Volume (MCV).
- Biochemistry: sodium, potassium, magnesium, chloride, glucose, urea, creatinine, eGFR, total protein, calcium, phosphorus, total bilirubin, unconjugated and conjugated bilirubin, Aspartate Amino Transferase (AST), Alanine Amino Transferase (ALT), alkaline phosphatase, Lactate DeHydrogenase (LDH). Triglycerides (TG).

Blood Urea Nitrogen (BUN) will be calculated on the basis of serum Urea values.

For all laboratory assessments, the site laboratory will flag laboratory values falling outside of the normal ranges on the site laboratory report (which the investigator should review and sign off) and the investigator will report any values considered clinically significant as an AE.

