## 2. EVALUATION CRITERIA

### 2.1. Demographic and other baseline characteristics

Demographic parameters are age, sex, race, ethnicity, childbearing potential, body weight, height, and body mass index (BMI). These parameters will be collected during the screening visit.

Baseline characteristics are:

- the medical history
- prior contrast agents
- prior medications
- the physical examination
- vital signs (systolic and diastolic blood pressure, pulse rate)
- blood samples collection

The laboratory data analysis will be performed by the site laboratory.

The following parameters will be assessed:

- Hematology: red blood cells (RBCs), white blood cells (WBCs), neutrophils, eosinophils, basophils, lymphocytes and monocytes, platelet count, hemoglobin, hematocrit, Mean red blood Cells Volume (MCV).
- Biochemistry: sodium, potassium, chloride, glucose, blood urea nitrogen (BUN) / urea, creatinine, creatinine clearance estimated by Cockcroft-Gault, eGFR (CKD-EPI), total protein, calcium, magnesium, phosphorus, total bilirubin, unconjugated and conjugated bilirubin, aspartate amino transferase (AST), alanine amino transferase (ALT), alkaline phosphatase, lactate dehydrogenase (LDH), triglycerides (TG).
- cardiac status from ECG exam (QT, QTcF, QTcB, QRS, PR, RR, heart rate, sinus rhythm).

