#### 2.3.1.2 *Laboratory data*

For each subject, blood samples will be collected before the first trial product administration and 2 days after each administration. The laboratory data analysis will be performed by the site laboratory. The following parameters will be assessed:

- Hematology: red blood cells (RBCs), white blood cells (WBCs), neutrophils, eosinophils, basophils, lymphocytes and monocytes, platelet count, hemoglobin, hematocrit, Mean red blood Cells Volume (MCV).
- Biochemistry: sodium, potassium, chloride, glucose, blood urea nitrogen (BUN) / urea, creatinine, eGFR (CKD-EPI), total protein, calcium, phosphorus, total bilirubin, unconjugated and conjugated bilirubin, aspartate amino transferase (AST), alanine amino transferase (ALT), alkaline phosphatase, lactate dehydrogenase (LDH), triglycerides (TG).

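### The SAP confines magnesium to screening, but the current protocol includes it at Day 1 and after every administration and commits to summarising that panel

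*SAP*

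**What the plan says.** **Protocol (Version 5.0, 31 August 2018).** Section 7.2.2.2 sets the sampling times: "blood samples will be performed at screening visit, at Day 1 and 2 days after each administration". It gives one chemistry panel for those samples, and magnesium is in it: "Biochemistry: sodium, potassium, magnesium, chloride, glucose, urea, creatinine, eGFR, total protein, calcium, phosphorus". Flow-chart footnote 4 repeats magnesium in the biology panel, which the chart schedules at screening and on D1, D3, D6, D9 and D12. Sections 8.1.3.1, 8.1.3.5 and 8.1.4 confirm the Day 1 baseline sample and the later draws. Section 11.3.8 says the analysis will present the section 7.2 laboratory results as raw data, change from baseline and shift tables. It takes as baseline the last value before the first product.

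**SAP (Version 2.0, 24 July 2018, based on protocol Version 4.0).** Section 2.1 includes magnesium among the baseline characteristics: "total protein, calcium, magnesium, phosphorus, total bilirubin". Section 2.3.1.2 keeps essentially the protocol's on-study sampling times, "blood samples will be collected before the first trial product administration and 2 days after each administration", but its panel goes straight from potassium to chloride and never names magnesium: "Biochemistry: sodium, potassium, chloride, glucose, blood urea nitrogen (BUN) / urea, creatinine, eGFR (CKD-EPI), total protein, calcium, phosphorus, total bilirubin". The Table 2 footnote says "Magnesium and creatinine clearance from Cockcroft-Gault method measured only at screening visit". Section 4, on changes from the protocol, does not mention magnesium. Section 5.6.4 lists and flags every recorded laboratory value, tabulates raw data and change from baseline, and adds shift tables.

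**The concern.** The two documents disagree on when a safety parameter is measured, and the disagreement carries through to what is reported. The SAP keeps sodium, potassium, chloride, calcium and phosphorus in the on-study list and leaves out magnesium without giving a reason. Low magnesium sits beside low potassium in the protocol's non-inclusion criterion 11, so it is a parameter the protocol itself singled out for this QT trial.

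At stake are the by-product magnesium summaries promised in protocol 11.3.8. The baseline is affected too. By the SAP 5.6.4 definition the baseline should be the Day 1 pre-dose value, but under the footnote only the screening value would exist.

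**Working it through.** The plan gives no figure to reproduce. The check sets the texts side by side and counts scheduled samples.

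1. **Scheduled magnesium samples per subject.**

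| Time | Protocol 7.2.2.2 and flow chart | SAP 2.3.1.2 and Table 2 footnote |
|---|---|---|
| Screening | yes | yes |
| Day 1, pre-dose | yes | no |
| Days 3, 6, 9, 12 (2 days after each administration) | yes, 4 samples | no |
| Total | 1 + 1 + 4 = 6 | 1 |

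2. **Values outside the SAP schedule.** The difference is 6 − 1 = 5 per subject.
   - With the 48 planned subjects: 48 × 5 = 240, made up of 48 Day 1 values and 48 × 4 = 192 post-dose values.
   - With 40 subjects, the evaluable number at which recruitment may stop (protocol 11.2): 40 × 5 = 200.

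3. **Is 240 a ceiling?** Yes. Withdrawals reduce it. The synopsis is also looser than the body of the protocol: its parameter heading names the selection visit and the post-dose draws but not Day 1. Read literally, that leaves the 192 post-dose values. Section 7.2.2.2, section 8.1.3.1 and the flow chart all include Day 1, so 240 is the count under the main text.

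4. **Is it a stray typing error in the SAP?** This is unlikely. The omission from 2.3.1.2, the inclusion in the 2.1 baseline list and the footnote all point the same way. The footnote does have a separate flaw. Its asterisk is also on the eGFR row, while its wording concerns Cockcroft-Gault clearance, and 2.3.1.2 lists eGFR (CKD-EPI) as an on-study parameter.

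5. **Is it a declared change?** No. SAP section 4 covers the number of timepoints tested, the removal of time from the model, the added heart-rate analysis and the PR and QRS thresholds. It says nothing about laboratory parameters.

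6. **Can it affect the QTcF result?** Magnesium is in neither the primary model (SAP 5.5.1.2) nor the concentration-response model (SAP 5.5.4.3). Holter recording ends 24 hours after dosing, and post-dose biology is drawn 2 days after dosing. No post-dose magnesium value is therefore contemporaneous with a Holter timepoint.

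**The case against.** The best case for leaving the SAP alone is that little would be lost. SAP 5.6.4 lists and flags all recorded laboratory values, and SAP section 7 lists everything in the case report form. Under protocol 7.2.2.2 the site laboratory flags out-of-range results and the investigator reports clinically significant ones as adverse events, which are tabulated by product. Magnesium is also a row of Table 2, inside the section whose general rule tabulates change from baseline and shifts. An analyst who held post-dose values could apply that rule.

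Most of this stands, and it limits the consequence. It does not remove the contradiction. Listings are not the change-from-baseline and shift tables that the protocol promises, and an analyst would have to go against both the footnote and the 2.3.1.2 list to produce them.

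A reader might draw three stronger conclusions that the documents do not support:

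- **That QT-relevant data would go unanalysed or be hidden.** Recorded values would still be listed and flagged. What is lost is the summary by product.
- **That a magnesium fall could explain a QTcF change and the plan would miss it.** The post-dose samples come after the Holter recording has ended. The documents also suggest no effect of P03277 on magnesium: the protocol introduction reports no clinically significant laboratory findings in the phase I/IIa trial.
- **That the values certainly exist, or that the origin of the mismatch is known.** The footnote speaks of measurement, so it could equally mean that magnesium was not assayed after screening. The Version 4.0 laboratory list is not available, so it is unknown whether the SAP departed from its source or was overtaken by Version 5.0.

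**Conclusion.** The SAP does not match the current protocol on magnesium, and the difference is undeclared. Followed as written, it would leave up to 240 scheduled values (200 with 40 subjects), five of the six per subject, out of the by-product summaries and shift tables to which protocol 11.3.8 commits. The count assumes that every subject completes all four periods and that the schedule in section 7.2.2.2 and the flow chart governs.

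The point is minor. It concerns one secondary safety parameter, individual values remain visible if recorded, and the primary QTcF analysis, assay sensitivity and stopping rules are untouched. Whether post-dose magnesium was actually collected is open on these documents, but either answer requires a correction: to the SAP's analysis if it was collected, or to its declared departures if it was not.

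**What to change.** Reconcile the SAP with protocol 7.2.2.2:

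- Add magnesium to the on-study biochemistry list in SAP 2.3.1.2.
- Remove magnesium from the Table 2 footnote, and correct the footnote's asterisk on the eGFR row in the same edit.
- Summarise magnesium by product like the other electrolytes: raw values, change from the Day 1 baseline, and shifts against the reference range.
- If magnesium was not assayed after screening, state that in SAP section 4 as a departure from the protocol and give the reason.

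If the protocol schedule was followed, the cost is one more parameter in tables already planned, with no new samples. If it was not, the cost is a short statement in section 4.
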